5.3 Provider Randomization Assignment Procedures

5.3.1 Randomization Procedures

Randomization will occur before the trial begins. All eligible providers will be block randomized to ensure comparable numbers of patients enrolled in each study arm. Providers will be categorized according to the expected number of patients for whom they will issue a qualifying prescription during the study period. The expected number of qualifying prescriptions will be determined given past prescribing behavior and department or specialty. Information on past prescribing behavior may vary across study sites based on available provider data but will generally include the absolute number of qualifying prescriptions as well as the rate of qualifying prescriptions (per number of visits billed or number of unique patients seen, as available). Providers in certain departments may also be more likely to write qualifying prescriptions. For example, providers who specialize in mental or behavioral health or providers in clinics focusing on higher risk adolescents. The particular departments associated with more qualifying prescriptions will be identified separately for each health system based on previous prescribing patterns and knowledge of that health system.

Providers in each health system will be divided into as few as two randomization blocks (likely and unlikely prescribers) and as many as four randomization blocks (unlikely, likely, high frequency, and very high frequency) based on the total number and distribution of expected number of qualifying prescriptions. For example, KP Washington providers wrote fewer than 100 qualifying prescriptions in the yearlong interval examined and the distribution of qualifying prescriptions per provider had a long right tail indicating that a small number of physicians wrote a large number of qualifying prescriptions. In this

context, we defined four groups for block randomization to protect against a large imbalance in the number of patients enrolled across study arms.

R, an open-source statistical computing software, will be used to generate an even number of control and intervention assignments within each provider block.

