All primary analyses will follow an intent-to-treat approach, including all individuals assigned to an intervention arm regardless of the amount of intervention received. Non-inferiority evaluations will also be evaluated in a supplementary “as treated” analysis, comparing outcomes according to treatments actually received by patients during their observed period of follow-up. This supplemental comparison is useful in a non-inferiority assessment due to the fact that the alternative hypothesis of “no effect” is more likely in the presence of protocol violations and therefore the intent to treat approach will be anti-

conservative if many patients in the intervention arm, for example, revert to control. Also, non-inferiority of Emergency Department visit rate in the intervention arm compared to usual care control will only be assessed on final analysis if superiority is shown for the primary endpoint of no antipsychotic use at 6 months.

We will use Poisson regression to estimate (1) the percent of individuals using antipsychotics at 6 months post enrollment and (2) the total number of person-months of antipsychotic use by youth in the six month follow-up period, per provider medication orders, in each of the study arms. We will use generalized estimating equations(43) to estimate the parameters in the Poisson regression model. We will use the robust sandwich estimator to ensure correct standard errors for the intervention effect due to possible violation of the Poisson variance assumption(44); additionally, this will allow us to account for any clustering within clinics(43) and providers. Poisson regression allows comparison of relative incident rates among the intervention arms when outcomes are not rare(45). Additionally, Poisson regression will allow us to control for pre-specified baseline covariates (age, gender, and race) as well as site differences in any antipsychotic use and allow for straightforward estimation of site-specific intervention effects in sensitivity analyses. For a secondary analysis, we will repeat this approach defining antipsychotic use with prescription fill data rather than orders.

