We will compare the outcomes of patients initially prescribed an antipsychotic medication from intervention providers versus control providers. We plan to conduct an intent-to-treat analysis i.e. if a patient is enrolled when an intervention provider issues a qualifying prescription, the patient is enrolled in the intervention arm and, even if the patient sees a control provider at some point, the patient will remain in the intervention arm. Intervention arm is a binary treatment assignment that should be indicated for all enrolled patients in the analytic dataset.

Baseline Covariates

Baseline covariates for this study include: age, gender, race, ethnicity, site, type of insurance (Medicaid/Commercial/Other i.e. self-paid), any inpatient hospitalization in the prior year, provider type and new health plan enrollee (defined as person who does not have 2 or more encounters at least 60 days apart in the year prior to their prescription order date). This definition of new health plan enrollee will be compared to an alternate definition in the three sites with health plan enrollment data: < 105 days enrolled in the health care plan before randomization date). Note that gaps in enrollment less than 45 days count towards the total of 105. Gaps in enrollment ≥ 45 days do not count towards the total of 105, nor does any enrollment prior to the gap ≥ 45 days. Any inpatient hospitalization in the prior year (-1 to -365 days from randomization date) will be adjusted for in primary analyses as it is prognostic of the outcome and will increase precision.

Health plan enrollment and follow-up time

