Inferential analysis for this outcome will estimate **the odds ratio (OR) of AP use observed at 6 months** between intervention and control. For this analysis, we will use a logistic regression model where the outcome is a binary indicator of AP use observed at 6 months. Binary treatment arm assignment and any inpatient hospitalization in the prior year will be the only covariates

Analysis plan for Safety Use of Antipsychotics in Youth (SUAY)

included in the regression model. The estimated coefficient associated with treatment is interpreted as the log-OR of observing AP use at six months for an intervention patient vs. a control patient. Patient is the unit of analysis, GEE will be used to account for correlation within provider, and robust standard errors (with working independence covariance matrix assumed) will be calculated to construct a 95% CI around the estimated OR. Our null hypothesis is that the OR is equal to 1, corresponding to no statistically significant difference between AP use observed at 6 months. We will reject the null hypothesis if the lower bound of the 95% CI is above 1 (increased use in treatment arm) or the upper bound is below 1 (decreased use in treatment arm).

Variables	Definition	Present/Absent
taking_at_6mon	Using AP at 6 months (No (0)/Yes(1))	present
groupn	Randomization Group - use for descriptive stats (Intervention (1)/Control(2))	present
group_cat	Randomization Group - use in models (Control (0)/Intervention (1))	present
prior_hosp	Prior Hospitalization (No (0)/Yes(1))	present

Sensitivity analysis will be conducted using similar approach as mentioned above, we will perform the following separate analyses related to our primary outcome by:

- % of patients taking antipsychotic medications (measured by orders) at 6 months post enrollment, using the minimum based on SIG reviews
- % of patients taking antipsychotic medications (measured by orders) at 6 months post enrollment, using the maximum based on SIG reviews
- % of patients taking antipsychotic medications (measured by prescription fills) at 6 months post enrollment. Note that this analysis may be performed using three healthcare systems (KPWA, KPCO, and KPNW) due to limitation in data availability

Variables	Definition	Present/Absent
taking_at_6mon_min	Using AP at 6 months - minimum (No (0)/Yes(1))	present
taking_at_6mon_max	Using AP at 6 months - maximum (No (0)/Yes(1))	present
taking_at_6mon_fills	Using AP (fills) at 6 months (No (0)/Yes(1))	present

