Descriptive analysis will summarize **the rate of AP use**, calculated as the days' supply (maximum of 181) ordered divided by follow-up time (time until end of enrollment or 181 days), Calculation of cumulative prescription fill ordered should be censored at 181 days. For example, if the only AP order for a patient is a 30 days' supply at, for e.g., 160 days post-enrollment, the total days' AP supply during follow-up should be recorded as 20 days (181 days -160 days) because we only want to capture AP use during the 6 months post-enrollment. In the case that total days' AP supply exceeds health plan enrollment that is, if a patient disenrolls from the health system with outstanding medication in hand, the total days' AP supply will include AP orders after disenrollment. For example, if a patient had an AP order after disenrollment on day 170 (a 30 days' supply), the total days' AP supply during follow-up should be recorded as sum of AP orders before day 170 and AP orders after day 170. Similarly, the offset should be increased to equal the last day with medication on hand (with a maximum for 181 for both).

Inferential analysis will estimate the **relative risk (RR) of AP use between intervention and control** during the 6 months post-enrollment. For this analysis, we will use Poisson regression where the outcome is the total days' AP supply (maximum of 181) for each enrolled patient and the offset is the number of days follow-up. For the primary analysis, treatment arm and inpatient hospitalization in the prior year will be the only covariates included in the regression model (additional covariate adjustment will be done as a sensitivity analysis), and the estimated coefficient for treatment arm is interpreted as the log-RR of AP use for an intervention patient vs. a control patient. Patient will be the unit of analysis for this regression model, and the regression model will be fit using generalized estimating equations (GEE) to account for correlation within provider. We will estimate standard errors using a robust (sandwich) covariance estimation (assuming a working independence covariance structure) and construct a 95% confidence interval (CI) around the estimated RR. Our null hypothesis is that the RR is equal to 1, corresponding to no statistically significant difference between AP order rates in

Analysis plan for Safety Use of Antipsychotics in Youth (SUAY)

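### Both primary models leave out site, the level within which providers were randomized, and the SAP gives no reason

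*SAP*

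**What the plan says.** **Randomization.** Each health system randomizes its own prescribers (protocol summary). Protocol 5.3.1 says "Providers in each health system will be divided into as few as two randomization blocks" and as many as four, by expected number of qualifying prescriptions, and that software will "generate an even number of control and intervention assignments within each provider block".

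**Protocol analysis (8.2.1).** "Poisson regression will allow us to control for pre-specified baseline covariates (age, gender, and race) as well as site differences in any antipsychotic use". The same sentence adds that the model will "allow for straightforward estimation of site-specific intervention effects in sensitivity analyses". The reference to sensitivity analyses thus attaches to site-specific effects, not to control for site.

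**SAP.** Under Baseline Covariates: "Baseline covariates for this study include: age, gender, race, ethnicity, site", among others. That section also says that prior-year hospitalization goes into the primary analyses, because it predicts the outcome and improves precision. Primary analysis I: "Binary treatment arm assignment and any inpatient hospitalization in the prior year will be the only covariates". Primary analysis II: "treatment arm and inpatient hospitalization in the prior year will be the only covariates included in the regression model", with the remark that "additional covariate adjustment will be done as a sensitivity analysis". For both outcomes the sensitivity analyses include models with site only, site and age, and site and the baseline covariates. No reason is given for keeping site out of the primary models.

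**The concern.** Site is a design factor: allocation was balanced inside each health system. The usual practice is to analyze as randomized, and the SAP's own criterion for a primary covariate (prognostic, improves precision) could well apply to site. The protocol foresees site differences in antipsychotic use, and the SAP does not say why site fails the criterion.

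Precision is at stake. If sites differ, chance differences between arms in the mix of sites stay in the estimate, and the standard error takes no credit for the within-site allocation. Readers will see a site-adjusted estimate, but the rejection rule in both primary analyses is tied to the confidence interval of the model without site. If the two disagree, the plan does not explain why that model decides.

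For days of use there is a further route. The SAP section on health plan enrollment and follow-up time fixes follow-up at 181 days at NCH, while at the other sites it can end at disenrollment. That may put a site difference into the measured rate even where true use is the same.

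**Working it through.** **1. The plan's own power figure.** The table in protocol 8.2.1 gives 92% power for 75% v 85% use with 360 per arm. With pooled null variance:

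- null SE = √(2 × 0.80 × 0.20 / 360) = 0.02981
- alternative SE = √((0.75 × 0.25 + 0.85 × 0.15) / 360) = 0.02958
- power = Φ((0.10 − 1.96 × 0.02981) / 0.02958) = Φ(1.405) = 0.920

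The figure reproduces. It contains no term for site or provider, so it is silent on this question.

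**2. Direction of the effect, independent patients.** Assume four equal sites, 1:1 within site, overall control use 85% and an odds ratio (OR) of 0.53 within site. Let r be the true variance of the unadjusted log-OR divided by its estimated variance. The actual size of the test is then 2(1 − Φ(1.96/√r)).

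- Site rates 78–91%: r = 0.98, size 0.048, power 0.904 without site v 0.907 with.
- Site rates 72–95%: r = 0.93, size 0.042, power 0.873 v 0.889.

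Omitting site makes the test slightly conservative.

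**3. With provider clusters, use at 6 months.** The documents give no site rates, intracluster correlation or provider count, so these inputs are assumed: 720 patients, four equal sites, four volume-ranked blocks per site with 1:1 allocation, 200 or 100 providers, lognormal patient volumes (log-SD 0.8 or 1.5), provider SD 0.3 on the logit scale, and prior hospitalization in 20% with log-OR 0.5. The analysis is logistic with a provider-clustered sandwich and working independence, 4,000 null and 4,000 effect runs per scenario. Each model is tested at the 5% cut-off from its own null runs. Power (%) is without v with site:

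| Control use by site (OR) | 200 / 0.8 | 200 / 1.5 | 100 / 0.8 | 100 / 1.5 |
|---|---|---|---|---|
| alike, 90% (0.50) | 86.7 v 86.2 | 79.1 v 78.7 | 82.8 v 81.7 | 74.0 v 72.5 |
| 55–70% (0.65) | 70.0 v 72.3 | 60.0 v 64.0 | 65.4 v 67.5 | 50.8 v 55.6 |
| 85–95% (0.50) | 81.6 v 83.7 | 67.9 v 76.6 | 78.0 v 81.7 | 62.3 v 71.8 |
| 45–75% (0.65) | 66.5 v 72.7 | 46.0 v 60.5 | 56.1 v 66.1 | 36.6 v 56.5 |

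The two moderate rows gain 2.1 to 9.5 points. The alike row changes by −0.4 to −1.5. With two blocks per site the moderate gain was 1.5–2 points (200 / 0.8) and 7–11 (100 / 1.5). With unequal sites (40/25/20/15%, 200 / 0.8) it was 1–2. The last row is a wide spread, shown for direction only.

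**4. The same models under the SAP's uncorrected 1.96 rule.** Type I error for use at 6 months was 3.5–8.6% without site and 5.4–9.8% with it. For days of use it was 4.7–9.1% and 5.8–10.5%. The high values come from few, uneven provider clusters and occur with either model; adding site makes them somewhat worse.

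**5. Site mix between arms.** Even allocation balances providers, not patients. The largest between-arm difference in one site's share of patients had a median of 7 points (90th percentile 12) at 200 / 0.8, and 20 (31) at 100 / 1.5.

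**6. NCH follow-up, days of use.** Suppose a share q leaves at uniformly distributed times, at NCH as elsewhere, and recorded use stops on leaving. Dividing by 181 instead of the actual follow-up lowers the NCH rate by q × 0.5: 5% at q = 10% (the overall loss in protocol 8.1), 2.5% at 5% and 10% at 20%. But Primary analysis II extends the offset to the last day with medication on hand and counts orders after disenrollment. If supply on hand at exit, s, is uniform over 0–30 or 0–90 days (assumed), the shortfall is q × E[(181 − s)²] / (2 × 181²). At q = 10% that is 4.2% or 2.9%. If leaving a plan does not end order capture at NCH, it is zero.

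**7. Room in the model.** At 95% v 89% use there are 360 × 0.05 + 360 × 0.11 = 57.6 non-users. Intercept, arm, prior hospitalization and three site terms make 6 coefficients, about 10 non-users each.

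**The case against.** **Site-adjusted analyses are already planned.** True for both outcomes, so no result would be missing. The dispute is only over which model carries the test. That limits the seriousness of the point but does not supply the missing reason.

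**The protocol makes no commitment.** Also true. It says what the model will allow, and it lists age, gender and race in the same breath. A reader might infer that the SAP breaks a protocol promise; the wording does not support that. The ground for site is the within-site randomization, which does not apply to age, gender or race.

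**By that logic the volume blocks belong in the model too.** In principle yes. But four sites with up to four blocks give up to 16 strata, hence 18 coefficients with arm, prior hospitalization and intercept: 57.6 / 18, about 3 non-users each. Site is the part that the data can carry.

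**Adding site worsens type I error under the stated rule.** This stands, and it is why the fix needs a corrected variance.

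**The size is assumed.** This stands. The 85%, 90% and 95% in protocol 8.2.1 are alternative overall control rates, not a spread between sites. The upper gains need very uneven provider volumes.

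**NCH.** A reader might infer that the NCH rate is 5% lower by construction. The documents do not support that: the offset extension reduces the figure, loss at NCH is not documented, and patients there need not be plan members to be seen. The rule is also the same in both arms, and a sensitivity analysis using the last encounter date already probes the follow-up definition.

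**Conclusion.** The point holds as a matter of precision and of an unexplained choice. Both primary models omit the level within which providers were randomized, and the SAP does not say why.

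The cost is about 2 to 10 points of power if site rates differ moderately (55–70% or 85–95% assumed) and about nil if they are alike. It rests on assumed provider numbers, volumes and site rates, so the real figure cannot be read from the documents. For days of use, the NCH follow-up rule may add a site difference of unknown size.

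Two stronger readings should be resisted. One is that leaving out site inflates false positives or invalidates the primary test; the calculation points the other way. The other is that site was dropped after results were seen. The SAP mentions an observed age difference between arms and carries edit dates in 2021, but it does not say when outcome results by arm became known.

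**What to change.** - Include site with prior hospitalization in both primary models. Justify it by the within-site randomization, not by observed differences between arms. Keep the model with arm and prior hospitalization as a sensitivity analysis.
- Base the primary test on a small-sample-corrected cluster sandwich variance, for example Mancl-DeRouen with a t reference. The power figures above were calibrated by simulation, not run with this correction, so check the corrected test once the provider count is known.
- Specify, blind to arm, how a site with almost no non-users is merged. With one small site at 95% use, 16 of 8,000 site-adjusted fits (0.2%) failed.
- If outcome results by arm are already known, leave the primary model in place, state why site was left out, and report the site-adjusted estimate beside the primary one for both outcomes.

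**Cost.** SAP wording; site is already in the dataset. The model gains three parameters. The odds ratio becomes conditional on site, with a log-OR 2–3% larger under moderate site differences. If sites are alike there is a small loss of power (up to 1.5 points in the table), which can be larger with few, very uneven clusters.

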groupn	Randomization Group - use for descriptive stats (Intervention (1)/Control(2))	present
group_cat	Randomization Group - use in models (Control (0)/Intervention (1))	present
site	Study site (KPCO (1)/KPWA (2)/KPNW(3)/NCH (4))	present
prior_hosp	Prior Hospitalization (No (0)/Yes(1))	present

- We will analyze outcome (orders) using adjusting for type of providers i.e. Mental Health (MH) providers in comparison to Non-Mental Health providers.

Variables	Definition	Present/Absent
taking_at_6mon	Using AP at 6 months (No (0)/Yes(1))	present

Analysis plan for Safety Use of Antipsychotics in Youth (SUAY)

groupn	Randomization Group – use for descriptive stats (Intervention (1)/Control(2))	present
group_cat	Randomization Group – use in models (Control (0)/Intervention (1))	present
prior_hosp	Prior Hospitalization (No (0)/Yes(1))	present
provider_type	Provider type of the enrolling provider, based on specialty (Non-Mental Health (0)/Mental Health (1))	present

- We will adjust for some baseline covariates in the model – site only, site and age (since significantly different by intervention and controls), and site and baseline covariates.

Variables	Definition	Present/Absent
taking_at_6mon	Using AP at 6 months (No (0)/Yes(1))	present
group_cat	Randomization Group (Control (0)/Intervention (1))	present
prior_hosp	Prior Hospitalization (No (0)/Yes(1))	present
site	Study site (KPCO (1)/KPWA (2)/KPNW(3)/NCH (4))	present
provider_type	Provider type of the enrolling provider, based on specialty (Non-Mental Health (0)/Mental Health (1))	present
age_emanicip	Emancipated age according to state (No (0)/Yes(1))	present
gendern	Gender (Male (1)/Female (2))	present
race_AA	Either race variable is African American/Black (No (0)/Yes(1))	present
race_AllOth	All other racial/ethnic groups (does not include white, black or unknown) (No (0)/Yes(1))	present
Hispanic	Hispanic ethnicity (No (0)/ Yes (1))	Present
insuranceType	Type of insurance Commercial/Medicaid/Other	present
new_enrollee_1	new health enrollee (1 st definition) Yes/No	present

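### Both SAP primary models drop the protocol's age, gender, race and site terms without explanation, although the SAP records an age difference between arms and codes age only as a yes/no flag

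*SAP*

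**What the plan says.** Protocol section 8.2.1 describes one Poisson approach for both primary outcomes and says that it "Poisson regression will allow us to control for pre-specified baseline covariates (age, gender, and race) as well as site differences in any antipsychotic use".

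The SAP lists age, gender, race, ethnicity and site under Baseline Covariates, but singles out prior-year inpatient hospitalization, which "will be adjusted for in primary analyses as it is prognostic of the outcome and will increase precision". The inferential model for Primary analysis I is then closed: "Binary treatment arm assignment and any inpatient hospitalization in the prior year will be the only covariates". Primary analysis II says the same: "treatment arm and inpatient hospitalization in the prior year will be the only covariates included in the regression model", with the remark that "additional covariate adjustment will be done as a sensitivity analysis".

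The sensitivity analyses for both primary outcomes add covariates in three steps: site only, then "site and age (since significantly different by intervention and controls), and site and baseline covariates". The age variable in the accompanying tables is age_emanicip, defined as "Emancipated age according to state (No (0)/Yes(1" (closing brackets omitted). The same flag stands for age in the exploratory heterogeneity-of-treatment-effect (HTE) tables of both primary analyses. No table lists age in years.

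**The concern.** The two documents give different primary models. The SAP says why prior hospitalization is kept. It does not say why the protocol's other terms were removed.

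The SAP also shows that baseline age had been compared by arm by the time the sensitivity plan was written, and that it differed. A covariate that the protocol names and the data show to be unbalanced is thus left out of the estimate that decides the trial.

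The design makes this more than a formality. Providers are randomized and patients enter afterwards. The randomization blocks use expected prescribing volume, not patient age (Protocol 5.3.1), and at the one site described a few providers write many of the prescriptions. Entry routes also differ by arm. An order for a study service is listed among the inclusion criteria (Protocol 5.2), the intervention alert defaults to keeping service orders (7.1), and only intervention providers can log a patient by ordering a service outside the alert (Appendix A). An age difference could therefore reflect who was enrolled, and not only chance.

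At stake is whether each primary estimate compares like with like, and whether the reported primary model is the one the protocol led readers to expect.

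**Working it through.** **Side by side.** No stated figure depends on this point, so there is none to reproduce.

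| Term | Protocol 8.2.1 | SAP primary I and II | SAP sensitivity | SAP exploratory HTE |
|---|---|---|---|---|
| Age | named | absent | yes/no flag | yes/no flag |
| Gender | named | absent | yes | yes |
| Race | named | absent | yes | yes |
| Site | named | absent | yes | not listed |
| Prior hospitalization | not named | included | included | included |

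**Smallest imbalance that would be called significant.** The anticipated numbers are 360 to 400 per arm (Protocol 8.1). For continuous age without clustering, the smallest significant difference is 1.96 × √(2/n) SD:

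- n = 360: 1.96 × √(2/360) = 0.146 SD
- n = 400: 1.96 × √(2/400) = 0.139 SD

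Clustering by provider would raise this threshold.

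**Shift in the treatment odds ratio if age is omitted.** To first order, factor = exp(imbalance × ln(OR per SD of age)). The OR per SD is an assumption (1.2 to 1.5), and the imbalance is taken as 0.14 or 0.3 SD.

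- 0.14 SD, OR 1.2: exp(0.14 × 0.182) = 1.026
- 0.14 SD, OR 1.5: exp(0.14 × 0.405) = 1.058
- 0.3 SD, OR 1.2: exp(0.3 × 0.182) = 1.056
- 0.3 SD, OR 1.5: exp(0.3 × 0.405) = 1.129

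The shift is therefore about 3-6% at 0.14 SD and 6-13% at 0.3 SD, in a direction the documents do not allow us to determine. The same formula holds for the rate ratio in Primary analysis II, with an assumed rate ratio per SD.

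**If the imbalance is in a yes/no age variable.** The smallest significant difference is 1.96 × √(2p(1−p)/n). At n = 360 it is 4.4 points for p = 10% and 7.3 points for p = 50%. With p = 50%, an imbalance of 7 to 15 points and an age-outcome OR of 1.25 to 2.0, omitting the variable moves a true OR of 1.00 to between about 0.985 and 0.90, or the reciprocal.

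**What a binary cut retains.** Under a normal approximation, the share of linear age information kept is φ(z)²/(p(1−p)), where p is the proportion above the cut:

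- p = 50%: 0.64
- p = 20%: 0.49
- p = 10%: 0.34

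To first order, the rest of the log shift survives adjustment for the flag. At a median cut, 0.36 × 0.14 × 0.182 = 0.009 and 0.36 × 0.14 × 0.405 = 0.020, so about 1-2% remains of the 3-6%. With 10% above the cut, 0.66 × 0.14 × 0.182 = 0.017 and 0.66 × 0.14 × 0.405 = 0.037, so about 2-4% remains.

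**The case against.** The strongest reply has five parts.

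1. **The protocol wording is soft.** It says what Poisson regression makes possible, which is less than a commitment to a model. That is fair, so a reader should not infer that the SAP breaks a binding specification. But the covariates are called pre-specified and a departure from them needs a reason.

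2. **Adjustment is already planned.** Three adjusted versions of each primary outcome are listed, and age also has an HTE interaction model. A reader might infer that age is confined to sensitivity models, or not handled at all. Neither is so. What stands is that the change of primary model is unexplained and that the age term used elsewhere is coarse.

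3. **Bias is not shown.** Omitting age distorts the estimate only if age predicts outcome, and chance imbalance from randomizing providers is already part of sampling error. The assumed shifts are small beside the planned effects: 89% vs 95% is an OR of (0.89/0.11)/(0.95/0.05) = 0.43, and 75% vs 85% is (0.75/0.25)/(0.85/0.15) = 0.53. This stands against any claim of known or large bias. It does not remove the concern, because enrolment after randomization can add imbalance that is not chance, and the decision rests on whether a 95% interval excludes 1.

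4. **Sequence.** A reader might infer that the covariates were dropped after the arms had been compared, or that only the protocol's set predates that comparison. The SAP gives several edit dates but does not say which text was written when. The two-covariate model may predate the age remark.

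5. **The flag may work better than feared.** If the recorded difference was in the flag itself, adjusting for it removes that difference. A reader might also infer that the flag is constant in states with a cut at 18, since all patients are younger than that. No state's cut is given, so this cannot be asserted.

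**Conclusion.** The point holds as an unexplained mismatch between the protocol and both SAP primary models, made more important by an age difference that the SAP itself records. Whether the sensitivity-plan remark about a significant difference covers age alone or site and age together, age is included.

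The size is unknown. The documents give no imbalance, no age-outcome association, no test used and no definition of the cut behind the flag. The 3-6% and 6-13% shifts rest wholly on an assumed OR of 1.2 to 1.5 per SD of age, on imbalances of 0.14 and 0.3 SD, and on the anticipated sample size without clustering. They show what is plausible and are not an estimate of bias in this trial.

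The planned sensitivity analyses reduce the risk but do not settle it. They do not bring the primary estimate into line with the protocol, and one cut across ages 3 to 17 can leave part of an age imbalance in place. The change is worth making because it is cheap, not because harm to the result has been demonstrated.

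**What to change.** - **Primary models (SAP, Primary analyses I and II).** Include age in years, gender, race and site beside arm and prior-year hospitalization. Give the protocol as the reason, not the baseline significance test, which is a poor basis for choosing covariates. Date the change and say that baseline data by arm had been seen.
- **Two-covariate model.** Keep it as a sensitivity analysis, so that readers can see what the restored terms do.
- **Age variable.** Use age in years instead of age_emanicip in the adjusted sensitivity models and the HTE models of both primary analyses. If the flag is kept for any purpose, state its cut in each state.

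The cost is SAP wording and a re-run. Gender, race and site variables are marked as present in the SAP tables. Age in years is not in those tables, but age had to be known to establish eligibility.

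There are two small downsides. The OR becomes conditional on more covariates, so part of any difference from the two-covariate OR would not be confounding. There are also more parameters. With two race indicators as the SAP lists them and three for site, the logistic model has arm 1 + hospitalization 1 + age 1 + gender 1 + race 2 + site 3 = 9. At 95% vs 89% use and 360 per arm, non-users number about 18 + 40 = 58, or 58/9 ≈ 6 per parameter. At 85% vs 75% they number 54 + 90 = 144, or 16 per parameter. If non-users are few, age should stay linear, without a spline.
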